Mammography and MRI results are typically classified in accordance with the American College of Radiology classification system, the Breast Imaging Reporting and Data System (BI-RADS) (www.acr.org; under Quality and Safety resources, BI-RADS atlas). A negative screening mammography is an inclusion criterion for this study, which means that per definition, all mammographic screenings have been classified as either BI-RADS 1 (=negative) or 2 (=benign finding). With the MRI assessment, the mammography results may be used, as well as those of previous examinations. The MRI assessments MRI BI-RADS 1 (=negative) and 2 (=benign finding) give no indication for further follow-up. These women are invited again after 2 years to take part in the population-based screening study. With MRI BI-RADS 3 (=probably benign abnormality), the MRI examination is repeated after six months. There is a positive finding with the MRI if it is classified as MRI BI-RADS 4 (=suspicious abnormality) or 5 (=highly suggestive of malignancy). These abnormalities will cytologically or histologically need to be confirmed. Women with a positive MRI result will undergo an ultrasound-guided or MRI-guided biopsy. The MRI BI-RADS 0 result (=incomplete examination) is merely a temporarily result, and completion of this examination will take place as soon as possible.

4. Technical realisation

MRI examinations are made no later than 8 weeks after participating in the population-based mammography screening program. For premenopausal women (women with at least 1 menstruation in the last 30 days), the MRI examination is scheduled between day 7 and 14 of the menstrual cycle as much as possible to avoid hormonal-induced enhancement.

All women in the MRI group will be scanned according to a "state-of-the-art" MRI protocol. Prior to the start of the trial, this protocol is standardised in the participating centres. The scans will be interpreted by experienced radiologists, using the under 3.3. referred to MRI BI-RADS criteria.

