population-based mammography screening program and for an MRI examination as part of this experimental population-based screening studv. With a BI-RADS 3 (=uncertain; probably benign abnormality) result, an MRI examination is repeated after six months. The radiology department will contact the woman for this examination. A positive MRI examination (BI-RADS 4 or 5) requires a cytologic or histologic evaluation. This is done using an ultrasound-guided biopsy, or if the abnormality cannot be traced with a second-look ultrasound, using an MRI-guided biopsy. Cytological and histological evaluation is reviewed in the concerning centres by experienced mamma-pathologists to determine the subsequent clinical strategy. Within the framework of this study, all the material will also be evaluated centrally later. If an abnormality, found using MRI, turns out not to be malignant following further examination, the woman is invited again after 2 years for another mammography as part of the current population-based screening program and for an MRI examination as part of this experimental population-based screening study. Part 4. Scientific appropriateness (max. 125 lines) 1. Efficacy The efficacy of adding MRI to the current breast cancer screening programme among women with very dense breasts is to this day unclear and is to be investigated in this experimental population-based screening study. There is, however, strong evidence from the literature that MRI could be worthwhile for these women. Different studies show that MRI can identify tumours missed by mammography and ultrasound (11-14). The value of MRI for screening purposes has been investigated among (young) women with a BRCA1 or 2 mutation or an otherwise very strong family history of breast cancer. Since young women have dense breasts more often, the results of these studies are important to this experimental population-based screening study. A recent meta-analysis of these studies (20) show a sensitivity of 94% (95%CI 90-97) for the MRI and mammography combined, and 39% (95%CI 37-41) for mammography only. The combination with MRI did result in more false positives than mammography only (specificity 77% 95%CI 75-80% and 95% 95%CI 93-96% respectively). Nevertheless, the specificity did improve in the following screening rounds. Although survival data are still not available, the more favourable staging of the tumours discovered by adding the MRI predicts a considerable reduction of breast cancer mortality rates. That is why the American Cancer Society advises to screen women with a high risk of developing breast cancer annually with MRI in addition to mammography. The first results of the ACRIN 6666 study among women with very dense breasts and an increased risk based on the Gail or Claus risk assessment models, where MRI is added after three years of screening with mammography and ultrasound support these results (23). This study shows that many more breast cancers at early stages are found by MRI compared to mammography and ultrasound and the combination of these two. This study also confirms that ultrasound screening or MRI leads to more false positive assessments and unnecessary biopsies than screening with mammography only.

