The participants are randomised by a computer-generated randomisation sequence, with stratification for screening centre. A screening centre is a radiologic partnership assessing the screening mammograms for a certain region.

Blinding

The proposed experimental population-based screening study is a pragmatic (in comparison to explanatory) trial whereby two different screening strategies, including possible placebo or external effects, are compared. The importance of blinding the outcome measure in a pragmatic trial depends on the 'hardness' with which the outcome measure can be determined. In this case, it concerns the presence of breast cancer (screening-detected and interval cancers), which will be assessed objectively with the help of histology. Thus, blinding in this trial is not necessary.

Starting and end date project Within this experimental population-based screening study, 3 screening rounds will be carried out in a period of 6 years. Because of the capacity at the MRI centres, it might be necessary to include the screening rounds in stages, we pursue a longer period for the entire study, namely from 1 September 2011 to 1 September 2019. However, the research period per participant is still 6 years. For every participant, the intervention in a following screening round is the same as in her first screening round, so independent of, for example, a possible change in breast density. Eventually sensitivity analysis will be carried out to find out whether this has possibly influenced the results.			
7. Sample siz	e, feasibility		
interval cance group. The as Team for Bre	size is calculated on a er percentage between ssumptions are based o east Cancer Screening kowske et al. (6) and a	the intervention gro on the report of the in the Netherland	oup and the control National Evaluation s 1990-2007 (1), a
screening exa between scree occurrence of extrapolation setting. The p detected tum	aged 49-50, there a aminations: 4.2/1000 b enings (interval cancer breast cancer in the c of the data collected by programme sensitivity ours divided by the r a screening interval o	y screening and 2/ s) (1). In the table k lifferent density cate Kerlikowske and e (calculated as the total of screen-de	1000 in the interval below, the expected egories is based on t al. (6) to the Dutch number of screen- tected and interval
Breast	Number of breast	•	Proportion

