The experimental population-based screening study will be integrated in the infrastructure of the Dutch population-based mammography screening program, which is national and entirely digital. We foresee to have to invite 7,237 women to be able to include 4,776 women (expected participation rate 66%) in the intervention group. The total study population (intervention and control group) will consist of 36,185 participants. The total target population of participants in the Dutch population-based mammography screening program with >75% density in the Netherlands is 90,000 in a period of 2 years, so we could expand our recruitment if the number of people participating is disappointing. We invite women living near the participating MRI centres (referred to in *Section 10. Organisation*). Every centre will have to make on average 400 extra MRI examinations per year for this experimental population-based screening study. The centres have already indicated their desire to participate.

8. Effectiveness of treatment and practice options

It is known that treating breast cancer in an early stage reduces the mortality rate. This is the motivation to conduct a population-based screening program on breast cancer in the Netherlands. The recently

updated meta-analysis from Nelson et al. (36) for the US Preventive Taskforce 2009 report confirms again that mammographic screening reduces the number of deaths due to breast cancer. The relative risk of dying because of breast cancer is lower among women invited for mammographic screening compared to women in a control group who are not invited for screening (50-59 years: 0.89 95%CI 0.75-0.99; 60-69 years: 0.68 95%CI 0.54-0.87). Furthermore, it is known that with mammographic screening, breast tumours among women with extremely dense breasts are diagnosed at a later stage compared to breast tumours among women with low density.
If we would be in the position to realise that same early detection among women with very dense breasts, it may be expected that this would reduce the number of deaths due to breast cancer. There are no indications thus far that breast tumours among women with very dense breasts have other intrinsic characteristics which would give them a more favourable or unfavourable prognosis (30;37).
9. Outcome analysis, evaluation

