In addition, the psychological consequences the experimental populationbased screening study could cause will also get attention by using the 'Consequences of Screening---Breast Cancer' (COS-BC) questionnaire (42). The first part of the questionnaire (COS-BC-1) asks specifically about the fears and uncertainties during the screening procedure. The second part of the questionnaire (COS-BC-2) aims to get the woman to look back at the entire period of examinations and have her assess whether it has brought about positive and/or negative changes. The great advantage of the COS-BC questionnaire in comparison to other validated anxiety questionnaires is the fact that it is focussed specifically on breast cancer screening. With three short questions, the screen-specific items questionnaire uncover the burden experienced by the MRI examination (43). The group of women with MRI-detected breast cancer will be asked to answer the EORTC questionnaire once (44). The goal of the quality of life analysis is to investigate the (changing) quality of life in the intervention arm as a whole. Besides, whether differences can be observed between participants with false positive, true positive, false negative and true negative MRI results will be addressed. The moments at which time the different questionnaires are conducted is indicated in the flowchart (see 'Flowchart timing of questionnaires'). Interim analyses The first analyses are carried out after the first screening round, namely: 1. When all women in the intervention group have received an MRI, including any possible diagnostic work-up. At that point, the extra number of tumours detected by the MRI, and missed by the mammography, can be estimated, as well as the recall rate, the positive predictive value and the number of biopsies per positive MRI test. 2. Two years after the last participant has been screened, the difference in the proportion of interval cancers is analysed and the tumour size and stage between both groups are compared. An interim analysis on the primary outcome is not possible, because information on interval cancers is only available after all participants have been screened and followed for two years. For the false-positive percentage, interim monitoring will take place. From the abstract from Berg et al. (23) on the added value of MRI in the ACRIN 6666 trial, it is possible to calculate that the percentage 'unjustified' referrals in the entire investigated group is 17% and the percentage 'unjustified' biopsies is 9%. Based on this, we have decided the following: If after the first 750 MRI examinations the number of unjustified referrals is more than 25% or the number of unjustified biopsies is above 15%, consultation on modification of the intervention in relation to the referral criteria is necessary and suspending the trial could be considered. A Data Safety and Monitoring Board is installed to this end, in any case consisting of an independent biostatistician, radiologist and oncologist as its members.

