There have been reports of Nephrogenic Systemic Fibrosis (NSF) among patients with severe kidney dysfunction (see FDA website: http://www.fda.gov/Drugs/DrugSafety/ucm223966.htm#aihp). NSF is not described with patients with normal kidney functions. Severe kidney dysfunction is therefore an exclusion criterion for this study.

2) With the MRI examination, there is a chance of a false positive result with uncertainty, followed by extensive further and possibly invasive examination. How often this will happen in this population is not known and is also subject of the trial. The best indication we have comes from a recently published abstract (23) on the MRI substudy of the ACRIN 6666 trial (10). This study shows that based on MRI, 17% of the participants underwent further examinations (imaging or biopsy) that were in retrospect unnecessary. Nine percent underwent, in retrospect, an unnecessary biopsy. Based on histopathological research, it turned out the abnormalities of these patients were benign.

Participants will be informed thoroughly on the increased probability of false positives. Unnecessary invasive examination will be avoided as much as possible by looking back at the original mammographic examination, by assessing the MRI BI-RADS 3 results centrally and by scheduling a follow-up MRI after 6 months for this category and finally, by carrying out a target ultrasound before a possible biopsy.

3) There is a chance at being diagnosed with a relative indolent tumour that would never have been noticed if an MRI screening had not taken place (overdiagnosis). Overdiagnosis is inherent to screening: in the Dutch population-based screening program it is estimated that about 8% of the breast tumours discovered by screening would never have been diagnosed clinically in the absence of a screening programme (47). There are no estimates known yet on overdiagnosis in high-risk groups screened by MRI. We do not expect the overdiagnosis percentage to be higher in our study compared to the current population-based screening program because the ductal carcinoma in situ (DCIS) that plays a central role in the overdiagnosis problem, is actually easier to detect with mammography than with MRI (25;26). Besides, Kuhl et al. (48) have shown that the sensitivity of MRI for DCIS is especially high for the high-grade lesions that are most likely clinically more relevant.

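### Does the 25% limit on unjustified referrals fall due at 750 MRIs before the six-month repeat scans make it readable?

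*Combined protocol and SAP*

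**What the plan says.** **The check.** Part 7, section 9 (Interim analyses) introduces interim monitoring of the false-positive percentage. The rule begins "If after the first 750 MRI examinations the number of unjustified referrals is more than 25" per cent, and has a second limit of 15% for unjustified biopsies. Crossing either one calls for consultation on the referral criteria, and suspension could be considered. A board with an independent biostatistician, radiologist and oncologist is set up for this.

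**Its reference.** Section 9 cites 17% unjustified referrals and 9% unjustified biopsies from an earlier MRI substudy. The risk text of Part 7, before section 12, describes the first figure: "17% of the participants underwent further examinations (imaging or biopsy) that were in retrospect unnecessary".

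**The pathway.** Part 3, section 6: "With a BI-RADS 3 (=uncertain; probably benign abnormality) result, an MRI examination is repeated after six months". Part 3, section 3 defines a positive MRI as BI-RADS 4 or 5 and adds: "Women with a positive MRI result will undergo an ultrasound-guided or MRI-guided biopsy".

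**A contrast within section 9.** The first-round yield analysis has an explicit closing rule: "When all women in the intervention group have received an MRI, including any possible diagnostic work-up". The 750-MRI check has none in the text available. The text directly after the monitoring paragraph was not available, so a definition there cannot be excluded.

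**The concern.** The reference rate covers imaging as well as biopsy. As the pathway is written, BI-RADS 4 and 5 go on to tissue diagnosis, so the main route to further imaging without biopsy is BI-RADS 3. Whether that referral was unnecessary is known only after the six-month repeat. If 750 MRIs are done in under six months, no repeat is available.

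Two readers could then give the board different tallies from the same data. One counts pending BI-RADS 3 women. The other leaves them out because nothing yet shows the referral to be unjustified. On the second count the 25% limit could not react to BI-RADS 3 results, however common they were, and the 15% biopsy limit does not see them either. Waiting for the repeats would mean scanning a sizeable part of the first round before the limit is read.

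**Working it through.** **Inputs.** Part 7, section 7 plans "to be able to include 4,776 women (expected participation rate 66" per cent) and states "Every centre will have to make on average 400 extra MRI examinations per year". Part 7, section 6 states "3 screening rounds will be carried out in a period of 6 years", with an overall period of 8 years. The MRI total reproduces: 0.66 × 7,237 = 4,776.

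**Pace.** No overall pace is printed, so it is derived.
- Three rounds in 6 years: 4,776 × 3 / 6 = 2,388 a year = 199 a month, which equals 2,388 / 400 = 5.97 centres. Intake over 2 years (8 − 6) gives the same: 4,776 / 2 = 2,388.
- Three rounds over 8 years: 4,776 × 3 / 8 = 1,791 a year = 149.25 a month.

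**Time to the 750th MRI, and the cost of waiting for all repeats.**

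| Pace | 750th MRI (month) | Share of the 750 past six months | All repeats due (month) | MRIs done by then |
|---|---|---|---|---|
| Even, 199 a month | 750 / 199 = 3.8 | 0% | 9.8 | 1,944 (41% of 4,776) |
| Even, 149.25 a month | 750 / 149.25 = 5.0 | 0% | 11.0 | 1,646 (34%) |
| Linear growth over 24 months, 4,776 × (t/24)² (assumption) | 9.5 | 102 / 750 = 14% | 15.5 | 1,995 (42%) |

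A six-month linear start-up to 199 a month puts the 750th MRI at 6.8 months: 199 × 6 / 2 = 597 are done by month 6, and (750 − 597) / 199 = 0.77. By month 0.77 about 199 × 0.77² / 12 = 10 women had been scanned, so 1.3% of the 750 are past six months. Any even pace below 750 / 6 = 125 a month also takes the 750th MRI beyond six months. So 'before any repeat' depends on full pace from the first day; 'before most repeats' holds in each row.

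**When the counting rule matters.** The limit is 0.25 × 750 = 187.5, crossed at 188. The chance of crossing is P(X ≥ 188) for a binomial with n = 750.
- At 17%: 1.5 × 10⁻⁸. At 9%: 3 × 10⁻³⁸. At the reference rates no way of counting crosses.
- The documents give no BI-RADS 3 share. Assume unjustified biopsies at 9% and add BI-RADS 3 shares of 10%, 14%, 16% and 20%. The total is 19%, 23%, 25% and 29%, and the chance of crossing is 0.00003, 0.097, 0.497 and 0.993. With BI-RADS 3 left out it is about 0 throughout.
- If the 9% lies inside the 17%, imaging without biopsy is 17 − 9 = 8 points. A total of 25% on these assumptions needs 16 points, twice that.

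**Effect of counting pending BI-RADS 3 women at once.** The overcount is at most the cancers among them. At the plan's 4.4 to 8.0 per 1000 that is 3.3 to 6.0 of 750 women, or 0.4 to 0.8 points. A tally that includes them is therefore available at 750 MRIs without waiting.

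**The case for a change.** The strongest case for a change is that the authors saw the need for completed work-up, since they wrote it into the first-round analysis, and left it out of the check next to it. Second-look ultrasound does not rescue the count, because in this pathway it leads on to biopsy. If BI-RADS 3 is excluded, the unjustified referrals are close to the unjustified biopsies, and a 25% limit adds little to a 15% limit on nearly the same women. On a wider count the result can swing from about 0 to 0.99 at a 20% BI-RADS 3 share. A few sentences would remove the doubt.

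Part of this stands: the term is undefined and the data cut unstated in the text available, and an immediate reading without pending women could be too low against its reference. The rest does not carry.
- The rule applies after the first 750 examinations. Its natural sense is that those 750 women are the denominator, judged once enough is known. 'Unjustified' is itself a retrospective label.
- Nothing instructs anyone to drop pending women.
- The rule monitors false positives, and the plan's positivity definition does not include BI-RADS 3. Work-up of BI-RADS 4 and 5 has no six-month wait.
- The documents do not say whether imaging in the 17% figure included a six-month repeat MRI, so no count can be shown to match it.
- Requiring every pending BI-RADS 3 result to count as unjustified is not a neutral clarification. It decides what trips the limit, as the 0 against 0.99 contrast shows.

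**Conclusion.** The timing observation is right at an even pace (3.8 to 5.0 months) and nearly right under a gradual start (1% to 14% of the 750 women past six months). It does not follow that the limit cannot be read. A tally with pending BI-RADS 3 women is available at once with under one point of overcount on the plan's cancer rates; a tally of BI-RADS 4 and 5 needs no repeat; a final tally can follow later.

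What is left is missing detail in a soft trigger handled by an independent board with statistical and radiological members. Such a board would ordinarily agree its definition and data cut beforehand, and could ask for the count with and without pending results. The choice affects the outcome only if the combined rate is near or above 25%, well over the 17% reference, and the BI-RADS 3 shares that produce this are assumptions. The primary comparison of interval cancers is not involved. The number of centres and the text directly after the rule were not available, which also argues against treating the gap as a fault. No change to the plan is called for.

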There have been reports of Nephrogenic Systemic Fibrosis (NSF) among patients with severe kidney dysfunction (see FDA website: http://www.fda.gov/Drugs/DrugSafety/ucm223966.htm#aihp). NSF is not described with patients with normal kidney functions. Severe kidney dysfunction is therefore an exclusion criterion for this study.

2) With the MRI examination, there is a chance of a false positive result with uncertainty, followed by extensive further and possibly invasive examination. How often this will happen in this population is not known and is also subject of the trial. The best indication we have comes from a recently published abstract (23) on the MRI substudy of the ACRIN 6666 trial (10). This study shows that based on MRI, 17% of the participants underwent further examinations (imaging or biopsy) that were in retrospect unnecessary. Nine percent underwent, in retrospect, an unnecessary biopsy. Based on histopathological research, it turned out the abnormalities of these patients were benign.

Participants will be informed thoroughly on the increased probability of false positives. Unnecessary invasive examination will be avoided as much as possible by looking back at the original mammographic examination, by assessing the MRI BI-RADS 3 results centrally and by scheduling a follow-up MRI after 6 months for this category and finally, by carrying out a target ultrasound before a possible biopsy.

3) There is a chance at being diagnosed with a relative indolent tumour that would never have been noticed if an MRI screening had not taken place (overdiagnosis). Overdiagnosis is inherent to screening: in the Dutch population-based screening program it is estimated that about 8% of the breast tumours discovered by screening would never have been diagnosed clinically in the absence of a screening programme (47). There are no estimates known yet on overdiagnosis in high-risk groups screened by MRI. We do not expect the overdiagnosis percentage to be higher in our study compared to the current population-based screening program because the ductal carcinoma in situ (DCIS) that plays a central role in the overdiagnosis problem, is actually easier to detect with mammography than with MRI (25;26). Besides, Kuhl et al. (48) have shown that the sensitivity of MRI for DCIS is especially high for the high-grade lesions that are most likely clinically more relevant.

Overdiagnosis cannot be assessed for an individual, but our research is set up to get a better understanding of the degree of overdiagnosis on a population level. If the total number of tumours discovered in the MRI group (screening tumours) is greater than in the control group but the number of

interval cancers does not decrease proportionally, this could be an indication of overdiagnosis.
12. Information, consent
The information and consent of the participants will be in accordance with the Central Committee on Research involving human subjects (in Dutch: Centrale Commissie Mensgebonden Onderzoek (CCMO)) regulations.
Potential participants for the experimental population-based screening study will be recruited via the Dutch population-based mammography screening program. After randomisation, the intervention group will receive an information package through the mail about the study, consisting of the following documents: a cover letter from the screening organisation, information for the participants with the consent form, flow chart, MRI examination questionnaire and the 'General medical scientific research with human subjects brochure'. In the cover letter, the women are asked – even if they are not interested in participating – to log in to the website www.juliuscentrum.nl/dense-studie . The login codes are provided in the information for the participants. If the woman is not interested in the study, the procedure is merely unregistering with an option to indicate the reason thereof. Women who do wish to participate in the study, register on the website and indicate they are interested in participating. Then the woman enters her personal data so she can be contacted by telephone by the research team. During this telephone conversation, the study is explained again and the woman has the opportunity to ask any remaining questions. If a woman decides to take part in the study, the study team employee will send the consent form to the MRI examination. If the woman indicates over the telephone to want more time to make a decision, a later time is agreed on to call again. An appointment is scheduled for the MRI examination for those women who do wish to participate in the study. The MRI appointment will be confirmed in writing.
The information flowchart is also annexed to the information for the participants.
13. Ethical assessment
Not submitted for approval by Medical Ethical Committee.
 14. Funding
